6.2 Pregnancies

Listing of participants who become pregnant while on study, with public ID, treatment arm, weeks of positive pregnancy test, weeks of study treatment discontinuation, and pregnancy outcomes

6.3 Mortality

Listing of participants who died, with public ID, treatment arm, primary cause of death, and weeks of death, and relationship to study treatment

6.4 Virologic failures

Table of N (%) of participants with virologic failure. If N is small, listing of virologic failures with public ID, treatment arm, weeks of initial and confirmed virologic failure, and HIV-1 RNA copies/mL at initial and confirmed virologic failure may be provided in lieu of summary table.

7 Arterial Inflammation

7.1 Inclusion/Exclusion for Efficacy Analyses

- 1) Table of N (%) of participants included or excluded, by reasons and treatment arm, in:
 - a. Efficacy set
 - b. Complete-case set
 - c. Supplementary set 1
 - d. Supplementary set 2

Inclusion/Exclusion for xxx Analysis Set					CVC (N=xxx)	Placebo (N=xxx)	Total (N=xxx)
Safety Population Flag	On-treatment for at least 12 weeks	Per-Protocol Population Flag	On-treatment for at least 22 weeks	No change in ART class from baseline			
Included	Included	Included	Included	Included	xx (xx%)	xx (xx%)	xx (xx%)
					xx (xx%)	xx (xx%)	xx (xx%)
					xx (xx%)	xx (xx%)	xx (xx%)
					xx (xx%)	xx (xx%)	xx (xx%)

7.2 TBR-related Outcomes

- TBRs will be \log_{10} -transformed for analyses and back-transformed to fold-change for interpretation and presentation.
- Missing data due to unreadable or missed week 24 scans will be handled using multiple imputation (MI) with regression (details will be provided in the AIP).

7.2.1 Descriptive Statistics for TBR Outcomes

Analysis set(s): Efficacy set

Stratification: Overall, by statin-use

Grouped by: Baseline, Week 24, Change

[figure not shown]
Analysis method: (change-outcomes only) stratified, within-arm paired two-sample t-test between baseline and week 24 with null hypothesis of no difference between baseline and week 24 TBRs.

Table	Columns for each group: Total (baseline group only), Cenicriviroc, Placebo	
Characteristic	Baseline, Week 24 Statistic(s)	Change Statistic
Index vessel MDS TBR	Mean (st.dev.), Median (Q1, Q3), and P10, P90	Mean, 95% confidence interval
Index vessel	N (%): Aorta, R Carotid, L Carotid	
Aortic Vessel TBR	Mean (st.dev.), Median (Q1, Q3), and P10, P90	Mean, 95% confidence interval
Bilateral Carotid Vessel TBR	Mean (st.dev.), Median (Q1, Q3), and P10, P90	Mean, 95% confidence interval

7.2.2 Figure of changes in TBR from Baseline to Week 24 versus participants

Analysis set(s): Efficacy set

Grouped by: by statin-use and treatment arm

7.2.3 Regression Analysis of Difference in Change in TBR between Treatment Arms

- Analysis set(s):
 1. Outcome: Efficacy set
 2. (Primary only) Sensitivity analysis: Complete-case set
 3. (Primary only) Supplementary analysis 1: Supplementary set 1
 4. (Primary only) Supplementary analysis 2: Supplementary set 2

- Analysis method:
 - Linear regression of change in TBR on treatment arm, adjusted by statin-use.
 - Linear regression above with interaction between treatment arm and statin-use.

NOTE: Linear regression with interaction (b) for secondary outcomes will be done only if linear regression with interaction of primary outcome shows that change in MDS TBR is different by statin-use.

Table	Regression Analysis Results		
Outcome	Characteristic	Summary Statistic(s)	Statistical Test
PRIMARY	Change in Index vessel MDS TBR (a)	Treatment parameter estimate	95% confidence interval, p-value
	Change in Index vessel MDS TBR given statin-use (b)	Treatment parameter estimate	95% confidence interval, p-value of interaction effect of statin-use
	Change in Index vessel MDS TBR given no statin-use (b)	Treatment parameter estimate	
Outcome	Characteristic	Summary Statistic(s)	Statistical Test
Secondary	Change in aortic vessel TBR (a)	Treatment parameter estimate	95% confidence interval, p-value
	Change in bilateral carotid vessel TBR (a)	Treatment parameter estimate	95% confidence interval, p-value

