- History of hypertension or blood pressure $\geq 130/80 \text{ mmHg}$ measured during screening
NOTE: See the A5415 Manual of Procedures (MOPS) for **blood pressure measurement guidance**.
- Elevated LDL cholesterol (fasting LDL of $>160 \text{ mg/dL}$; result from sample taken within 90 days prior to study entry can be used)
- Low HDL cholesterol ($<40 \text{ mg/dL}$; result from sample taken within 90 days prior to study entry can be used)
- Smoking (any current tobacco smoking)
- Family history of premature CAD (first degree relative with CAD prior to age 55 for male relative and 65 for female relative; participant report is acceptable)
- hsCRP $>2.0 \text{ mg/L}$ within 90 days prior to study entry without an active infection or acute illness at the time the sample was obtained

4.1.7 The following laboratory values obtained within 90 days prior to study entry by any US laboratory that has a CLIA certification or its equivalent, or at any network-approved non-US laboratory that operates in accordance with Good Clinical Laboratory Practices (GCLP) and participates in appropriate external quality assurance programs.

- Absolute neutrophil count (ANC) $>750/\text{mm}^3$
- Platelet count $>100,000/\text{mm}^3$
- Aspartate aminotransferase (AST) (SGOT) $\leq 5x$ upper limit of normal (ULN)
- Alanine aminotransferase (ALT) (SGPT) $\leq 5x$ ULN
- Alkaline phosphatase $\leq 5x$ ULN
- Estimated glomerular filtration rate (GFR) $\geq 60 \text{ mL/min}/1.73 \text{ m}^2$ as calculated using the Chronic Kidney Disease Epidemiology Collaboration (CKD-Epi) equation

NOTE: See the A5415 MOPS for further information and a link to the CKD-Epi equation and calculator.

4.1.8 Pre-entry FDG-PET/CT imaging (within 60 days prior to study entry) that has been deemed:

- Interpretable as assessed by the central imaging core laboratory
AND
- Without incidental findings that will preclude participation in the study at the discretion of the site investigator

4.1.9 No plans to receive immunizations 7 days prior to the week 24 study visit.

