10.4 Sample Size and Accrual

The target sample size is 75 participants (50 in the CVC arm and 25 in the placebo arm) with baseline and follow-up PET/CT. To allow for some loss to follow-up and participants unwilling or unable to complete 2 scans, we plan to enroll 93 participants (62 in the CVC arm and 31 in the placebo arm) in this trial.

The primary analysis will focus on between-treatment arm differences in the within-participant changes in arterial MDS TBR (the measure of arterial inflammation by PET/CT). Based on a superiority trial design with two-sided $\alpha=0.05$, assuming a standard deviation (SD) of $0.065 \log_{10}$ TBR for change in MDS TBR, a total of 75 participants providing complete, evaluable data sets will ensure 80% power to detect a between-groups difference of $0.046 \log_{10}$ MDS TBR (which is a 10% reduction from baseline).

The assumptions underlying the power calculation are as follows:

- 1) The target effect size for the change in MDS TBR on therapy of 10% is based on the observation of a statin intensification study [46].
- 2) The assumed SD for change in (\log_{10}) MDS TBR of 0.065 is derived from the placebo arm of ACTG A5314.
- 3) The use of a two-sided, two-sample T-test with type-I error rate of 5%.

The assumption that 93 enrolled participants will provide 75 participants with evaluable data is derived by 20% total data loss due to drop-out after randomization (including premature discontinuation of study treatment and change in background ART drug class).

If the variability in the change in MDS TBR is lower than assumed (smaller SD) or the total data loss is lower than assumed, the statistical power to detect the targeted effect size for our primary analysis will be higher (see Table 10.4-1).

Table 10.4-1: Sample Sizes and Power Corresponding to Various Total Data Loss and Assumed SD

Total sample size	Total data loss	Evaluable sample size	Power	Assumed SD for change in MDS TBR (in \log_{10})
93 (62 + 31)	20%	75 (50 + 25)	80%	0.065
108 (72 + 36)	20%	87 (58 + 29)	80%	0.071
93 (62 + 31)	20%	75 (50 + 25)	85%	0.061
93 (62 + 31)	17%	78 (52 + 26)	83%	0.065

For secondary outcome measures (excluding the secondary imaging measures), the sample size of N=93 will provide 90% power to detect a 0.052 SD difference. This

assumes a 15% total data loss (lower since there will be no loss due to image scheduling or quality related issues).

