10.6.2 Primary Analyses

The primary analysis of efficacy will be limited to the per-protocol population.

TBR will be transformed for analyses on the \log_{10} scale and back transformed to percentage change for interpretation and presentation. Change in TBR will be summarized by mean and 95% confidence interval for percentage for each treatment arm and compared between the arms using a T-test, stratified by statin

use. A 95% confidence interval for the relative between-arm shift will also be estimated.

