Geometric mean fold change (expressed as a percentage) in arterial MDS TBR after 24 weeks of treatment with and without CVC.	Fold change in TBR (1 - the geometric mean change) will be summarized by treatment groups with a 95% confidence interval. The relative treatment difference will be described as a geometric mean difference (active compared to placebo) and compared with a linear regression, stratified by statin use.
A supplementary analysis to the primary analysis will include participants who remain on treatment for at least 12 weeks and remain on the same ART drug class. A second supplementary analysis will exclude participants with confirmed HIV-1 RNA > 200 copies/mL or ART interruption for 14 or more consecutive days at any time during the course of the study.	

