2.4 Overview of Sample Size Considerations

The target sample size is 75 participants (50 in the CVC arm and 25 in the placebo arm) with baseline and follow-up PET/CT. To allow for some loss to follow-up and participants unwilling or unable to complete 2 scans, the study planned to enroll 93 participants (62 in the CVC arm and 31 in the placebo arm). Final enrollment was 110 participants.

The primary analysis will focus on between-treatment arm differences in the within-participant changes in arterial MDS TBR (the measure of arterial inflammation by PET/CT). Based on a superiority trial design with two-sided $\alpha=0.05$, assuming a standard deviation (SD) of 0.065 \log_{10} TBR for change in MDS TBR, a total of 75 participants providing complete, evaluable data sets will ensure 80% power to detect a between-groups difference of 0.046 \log_{10} MDS TBR (which is a 10% reduction from baseline).

The assumptions underlying the power calculation are as follows:

- 1) The target effect size for the change in MDS TBR on therapy of 10% is based on the observation of a statin intensification study.
- 2) The assumed SD for change in (\log_{10}) MDS TBR of 0.065 is derived from the placebo arm of ACTG A5314.

3) The use of a two-sided, two-sample T-test with type-I error rate of 5%.

The assumption that 93 enrolled participants will provide 75 participants with evaluable data is derived by 20% total data loss due to drop-out after randomization (including premature discontinuation of study treatment and change in background ART drug class).

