3.1 Key Definitions Related to FDG-PET Imaging

Term(s)	Definitions at a Participant Level
Target vessel	Specific arterial vessels of interest: R carotid, L carotid, and aorta.
Background vessel	Internal jugular vein (JV) for carotids and superior vena cava (SVC) for aorta.
Standardized Uptake Value (SUV):	Decay-corrected tissue concentration of FDG (in kBq/mL) divided by the injected dose per body weight (kBq/g). SUV is unitless. 1. Target SUV 2. Background SUV 3. Average background SUV
Most diseased segment (MDS)	2-3 slices of arterial segment, centered on the slice of the target vessel with the highest SUV at baseline .
Index Vessel	Vessel with the highest vessel TBR (see definition below) at baseline (i.e., most diseased vessel).
Target-to-Background Ratio (TBR):	Measure of FDG uptake, calculated as a ratio between the target and background SUV. 1. Vessel TBR 2. Vessel MDS TBR 3. Index vessel MDS TBR

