7.3 Correlates of MDS TBR of the Index Vessel

These analyses are planned for the Final Report.

- Analysis set(s): Efficacy set
- Outcomes: 1) Baseline MDS TBR of the index vessel 2) Change in MDS TBR of the index vessel
- Covariates: Age, sex, race, BMI, use of statins at entry, ART (INSTI vs NNRTI), perceived stress scale, diet, average CVC trough (analysis of change only)

With the exception of average CVC trough, all measures are at entry. In the event of a positive effect of CVC, analyses of change will be limited to participants in the CVC arm.
- Analysis method:
 - Descriptive graphic displays of the distribution TBR by each of the covariates of interest
 - Linear regression of TBR adjusted for each covariate in turn (i.e., unadjusted analyses).

Analyses of change in MDS TBR will also adjust for baseline MDS TBR.
 - Linear regression of TBR adjusted for each covariate with evidence of association with TBR in unadjusted analyses. Given the relatively small sample size, evidence of association will be judged with either relaxed type 1 error or clinically meaningful effect sizes.
- Presentation of results: Forest plot for each outcome showing parameter estimates and 95% confidence interval.

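### Baseline TBR is left out of the primary change-score regression; the plan is valid without it, but adding it is a nearly free gain in precision

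*SAP*

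**What the plan says.** The primary comparison is described in three places, none of which includes baseline TBR:

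- SAP 7.2.3, model (a): "Linear regression of change in TBR on treatment arm, adjusted by statin-use". Model (b) adds only the arm-by-statin interaction.
- SAP 2.3.1, analysis approach: arms are "compared with a linear regression, stratified by statin use".
- Protocol 10.6.2: change in TBR is "compared between the arms using a T-test, stratified by statin" use.

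The baseline value is nevertheless always there. Protocol 4.1.8 makes a pre-entry scan an entry criterion and requires it to be "Interpretable as assessed by the central imaging core laboratory". SAP 7.2 foresees missing data only from week-24 scans.

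The SAP does use the adjustment elsewhere. For the correlates analyses in 7.3 it states "Analyses of change in MDS TBR will also adjust for baseline MDS TBR". No reason is given for leaving it out of the primary model.

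The same model form carries over to the sex and race repeats (SAP 7.2.4), the SUV outcomes (7.4) and the biomarkers (section 8).

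**The concern.** Regressing change on arm and statin use is the same as regressing the week-24 value on arm, statin use and baseline, with the baseline coefficient forced to equal 1. Measurement error and regression to the mean usually make the best-fitting coefficient smaller than 1. Estimating it then removes variance that the change score leaves in the residual.

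Only precision is at stake: the width of the primary confidence interval and the power of the primary test. Bias and type I error are not affected by leaving baseline out. The question still matters because the placebo arm supplies only about 25 to 29 evaluable participants.

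**Working it through.** **Inputs from the documents.** Protocol 10.4 and SAP 2.4 give a difference of 0.046 log10 TBR, an SD of change of 0.065, a two-sided 5% two-sample t-test, 50 + 25 evaluable, and 20% data loss. SAP 2.4 adds: "Final enrollment was 110 participants".

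**Assumed.** The correlation r between baseline and week-24 log10 TBR, and the SD at each visit, are not in the documents. Every r below is an assumption. The change SD is held at 0.065 throughout.

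**Step 1: the plan's own power (noncentral t).** SE = 0.065 × √(1/50 + 1/25) = 0.01592. Noncentrality = 0.046 / 0.01592 = 2.889 on 73 df. Power is 81.4%, or 81.3% after one df for statin use; the plan states 80%. The other rows of protocol Table 10.4-1 give 80.4% (stated 80%), 85.9% (85%) and 82.9% (83%). The sizing therefore matches the unadjusted change score.

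**Step 2: actual enrolment.** 110 × 0.8 = 88, or about 59 + 29. SE = 0.065 × √(1/59 + 1/29) = 0.01474, noncentrality 3.12, power 87.0%.

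**Step 3: adding baseline, ignoring vessel selection.** With equal variances at the two visits, residual SD = 0.065 × √((1 + r)/2), with one further df spent.

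| r | Residual SD | CI width vs unadjusted | Power 50 + 25 | Power 59 + 29 |
|---|---|---|---|---|
| 0.95 | 0.0642 | 0.987 | 82.3% | 87.8% |
| 0.90 | 0.0634 | 0.975 | 83.2% | 88.6% |
| 0.70 | 0.0599 | 0.922 | 87.1% | 91.7% |
| 0.50 | 0.0563 | 0.866 | 90.8% | 94.5% |

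**Step 4: adding baseline, with vessel selection.** SAP 3.1 takes as index vessel the one of three (right carotid, left carotid, aorta) with the highest TBR at baseline. Selecting a maximum compresses the spread at baseline relative to week 24. Change is then less strongly related to baseline, and the gain is smaller than in step 3. Trials were simulated (20,000 per setting, 40% statin users assumed) with the highest of three vessels selected at baseline:

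| r | 50 + 25: unadjusted → adjusted | Gain (points) | CI narrowing | 59 + 29: adjusted |
|---|---|---|---|---|
| 0.85–0.91 | 81–82% → 82–83% | 0–1 | −0.3% to 1.2% | 87–88% |
| 0.66–0.76 | 81–82% → 83–85% | 1.5–3.7 | 1.2–4.5% | 88–90% |
| 0.53–0.60 | 81–82% → 85–87% | 3.6–5.5 | 4.3–7.1% | 90–91% |

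Unadjusted power at 59 + 29 is 86–87%. A negative narrowing means a slightly wider interval. Monte Carlo error is about √(0.82 × 0.18 / 20,000) = 0.3 point. Type I error was 4.7–5.2% with and without baseline.

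**Step 5: worst case.** With an uninformative baseline, simulated power fell from 81.7% to 81.2% (50 + 25) and from 86.8% to 86.4% (59 + 29). The formula in step 3 counts only the lost df. The simulation also carries the cost of chance imbalance in baseline between the arms.

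**The case against.** The strongest reply is that nothing here is wrong. Change score and baseline-adjusted change are both legitimate. The design power is met, and over-enrolment has already raised it to about 87% if the planned loss holds. If r is near 0.9 the gain is negligible and the interval could even widen by 0.3%. All of this stands, and it is why the point is an improvement and not an error.

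Other objections stand in part:

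- **r is unknown.** Protocol 2.1 gives aortic TBR cut-offs from another trial, from which a baseline SD can be back-calculated. The 95% interval for that SD, 0.032 to 0.305 on the log10 scale, is far too wide to fix r. Putting its lower limit into 1 − 0.065²/(2 × SD²) gives an impossible −1.06, and its upper limit gives 0.98. The figure should not be used to choose among the rows above.
- **The selection model is approximate.** The SAP selects on vessel TBR and then analyses that vessel's MDS TBR, whereas the simulation selects on the outcome itself. Selecting on an imperfect proxy gives somewhat larger gains, so the step 4 figures are if anything conservative. They also depend on the correlation between vessels, so they should be read as bands.
- **Multiple imputation is not modelled.** The imputation details are left to the AIP, so whether baseline enters there cannot be seen. An imputation model does not replace a term in the analysis model.
- **SAP 7.3 has a different purpose.** It is a correlates analysis, limited to the CVC arm if CVC works. It shows that the term is practicable, not that the primary analysis must contain it.
- **Timing is late.** Accrual closed on 5 January 2024, so 24 weeks plus the 14-day window ends about 5 July 2024. SAP 2.0 is dated 18 July 2024. A further change to the primary model is credible only before unblinding and with a date on it.

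**Conclusion.** The point holds as an optional gain in precision. The planned model is valid as regards the missing covariate and meets its design power. With the index vessel selected at baseline, adjustment adds between nothing and about 5.5 power points at 50 + 25 over r from 0.91 down to 0.53. The change in interval width runs from 0.3% wider to 7% narrower. The most it is likely to cost is about half a power point. The balance favours adjustment, although its actual size cannot be known from the documents.

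This rests on an SD of change of 0.065, the assumed values of r, and an approximate model of vessel selection. No size is claimed for SUV or biomarkers. The statement that the model is valid concerns only the omission of baseline. The efficacy set is per-protocol, so exclusions after randomisation could leave the arms unequal in baseline TBR. Adjustment would help with that particular imbalance but would not repair per-protocol selection in general.

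**What to change.** Before unblinding, change SAP 7.2.3 model (a) to:

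`change in log10 index-vessel MDS TBR ~ treatment arm + statin use + baseline log10 index-vessel MDS TBR`

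Add the same baseline term to model (b) and to the sex and race repeats in 7.2.4, and the matching baseline value to each secondary change model. Keep the model without baseline as a sensitivity analysis. Bring SAP 2.3.1 into line and note the departure from the stratified t-test in protocol 10.6.2.

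If the data have already been unblinded, leave the primary model as it is and report the adjusted model as supplementary only.

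The cost is a dated SAP revision and one degree of freedom per model. SAP 2.0 has already moved from a t-test to regression, so the structure is in place. No new data are needed and no eligible participant is lost: the baseline scan is required for entry, and the biomarker analyses already need paired values.

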10.3 Randomization and Stratification

At study entry, participants will be randomized at a 2:1 ratio (CVC arm: placebo arm), using permuted blocks stratified by statin use. Institutional balance will not be used at randomization.

While enrollment is ongoing, enrollment limits will be increased to replace participants who are randomized but do not start treatment.

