1.1	Reviewed for Protocol version 2.0 with no changes needed.	Apr 15, 2024
2.0	
Section 2:
 
Removed details on Interim monitoringIn Section 2.3.1, clarified outcome measure description (most diseased vessel) and revised analysis approach to use linear regression instead of t-test.Added Section 2.3.3: exploratory analyses.Added Section 2.6: regarding timing of final analyses. 
Section 3:
 
Added Section 3.1: Key definitions section.Revised Section 3.1 for clarity, updated to Section 3.2.Revised Section 3.2 to include other outcome measures and to update presentation structure into table-list. Updated to Section 3.3 
Section 4.1:
 
Added Section 4.1.1 and 4.1.2: key dates and data inclusion/exclusion for data to be analyzed.Revised Section 4.1.3 (previously 4.1): updated Day 1, week 4, and week 22 definition/range. Updated baseline definitions for outcomes to be based on entry instead of pre-entry/entry.In Section 4.1.4 (previously 4.2.1): added complete-case set definition.Revised Section 4.2: cleaned up sentences and moved details to be in Section 5. 
Section 5:
 
Added protocol deviation table to be reported.Modified components of baseline characteristics summary.Updated summary measures for baseline characteristics, study status, and treatment status from continuous to categorical.Added analysis set to be used, groups, statistical tests, and other details relevant to each table to be generated.Added sections on all listed outcomes and associated details.	July 18, 2024

1 Introduction

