4.2 Analysis Approaches

- Descriptive summaries in Section 5 will be presented for both the Safety set and Efficacy set, unless otherwise specified.
- Summary statistics for discrete and continuous outcomes will be detailed under each report-content in Sections 5 - 9.
- All statistical tests will be two-sided with a nominal alpha level of 0.05.
 - No adjustment for multiple testing will be performed.
- Stratification will be taken into account in efficacy outcome analyses unless stated otherwise.
- No statistical comparisons across groups for baseline characteristics are planned.
- Missing data for TBR analyses will be handled using multiple imputation; sensitivity analyses will be complete case where missing data are ignored.
- Missing data for biomarker analyses will be ignored (i.e., all analyses will be complete case).

Report Contents

5 Participant Characteristics and Disposition

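### The primary regression names no variance estimator; in a 2:1 trial the default pooled standard error is biased if the arms differ in the SD of change, most plausibly in the conservative direction

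*SAP*

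**What the plan says.** SAP 7.2.3 gives the primary model (a) as "Linear regression of change in TBR on treatment arm, adjusted by statin-use". The estimand table in SAP 2.3.1 says the arms are "compared with a linear regression, stratified by statin use". The SAP version history records the change made in version 2.0: "revised analysis approach to use linear regression instead of t-test". SAP 4.2 sets the error rate: "All statistical tests will be two-sided with a nominal alpha level of 0.05".

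On allocation, Protocol 10.3 states that "participants will be randomized at a 2:1 ratio (CVC arm: placebo arm), using permuted blocks stratified by statin use". On planning, SAP 2.4 says "The target sample size is 75 participants (50 in the CVC arm and 25 in the placebo arm) with baseline and follow-up PET/CT" and claims "80% power to detect a between-groups difference of 0.046" on the log10 TBR scale. One SD serves both arms; Protocol 10.4 says the value "of 0.065 is derived from the placebo arm of ACTG A5314".

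Neither document names a robust standard error, an arm-specific residual variance or a check of the arm variances. The sensitivity and supplementary analyses in SAP 7.2.3 change the analysis set or the handling of missing scans, not the variance estimator. The change column of the table in SAP 7.2.1 shows a mean and 95% interval by arm, without an SD. SAP 1.1 leaves coding detail to an Analysis Implementation Plan, and SAP 7.2 leaves the multiple-imputation detail to it. That plan is not among the documents.

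**The concern.** Ordinary regression estimates one residual variance, weighted towards the larger arm. The true variance of the difference in means depends more heavily on the smaller arm. With 1:1 allocation the two effects nearly cancel; with 2:1 they do not.

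The plan gives some reason to expect unequal spread. The planning SD describes change on placebo. The CVC arm would add person-to-person variation in response if CVC works. The plan itself looks for such variation: SAP 9.1.3 correlates CVC trough with index vessel TBR, SAP 7.3 lists trough as a covariate for change, and SAP 7.2.3 and 7.2.4 test modification by statin use, sex and race. Protocol 2.1 reports a 29% lower CVC AUC with dolutegravir and, in an earlier phase 2 study, a lower share of proton pump inhibitor users reaching the target trough (84.5% against 94.3%).

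At stake is the calibration of the primary interval and p-value, and some power. The point estimate is not affected.

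**Working it through.** **Inputs.** From the documents: 2:1 allocation; 50 + 25 evaluable; effect 0.046 log10 TBR; SD 0.065; two-sided 5% level; 110 enrolled; 20% data loss. The last two give 110 × 0.8 = 88 evaluable, about 59 + 29. Assumed, because the documents do not give them: the ratio r of the CVC SD to the placebo SD, and 50% statin use.

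**1. The plan's own power.** SE = 0.065 × √(1/50 + 1/25) = 0.0159. The noncentrality is 0.046/0.0159 = 2.89 on 73 df, giving power of 81.4%. The stated 80% is reproduced under equal variances.

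**2. Bias of the pooled standard error at 50 + 25, in units of placebo variance.**
- True variance of the difference: r²/50 + 1/25.
- Expected pooled estimate: [(49r² + 24)/73] × (1/50 + 1/25).
- r = 1.25: true 0.0713, pooled 1.378 × 0.06 = 0.0827. SE ratio √(0.0827/0.0713) = 1.08, so large-sample type I error is 2Φ(−1.96 × 1.077) = 3.5%.
- r = 0.8: true 0.0528, pooled 0.758 × 0.06 = 0.0455. SE ratio 0.93, so type I error is 6.9%.

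**3. Simulation of change on arm plus statin use at 59 + 29.** There were 100,000 runs for type I error and 40,000 for power, on complete data without imputation. OLS is the ordinary pooled standard error. The placebo SD is held at 0.065.

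| CVC/placebo SD | Type I: OLS | HC2 | HC3 | Power: OLS | HC2 | HC3 |
|---|---|---|---|---|---|---|
| 0.8 | 6.8% | 5.3% | 4.8% | 93.0% | 90.7% | 90.0% |
| 1.0 | 4.9% | 5.1% | 4.6% | 87.2% | 87.2% | 86.2% |
| 1.25 | 3.5% | 5.0% | 4.6% | 76.6% | 80.9% | 79.8% |
| 1.5 | 2.6% | 5.0% | 4.6% | 63.6% | 73.4% | 72.2% |

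At 50 + 25 the pattern is the same. With r = 1.25, type I error is 3.6% with OLS, and power is 69.3% (OLS), 74.3% (HC2) and 72.8% (HC3). Over ratios from 0.5 to 2, type I error stays at 4.5–5.2% with HC3 and 4.9–5.8% with HC2.

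**4. The role of allocation.** With 38 + 37 and r = 1.5, OLS type I error is 4.95%. The 2:1 split drives the effect.

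**5. What the ratios mean.** If individual CVC effects vary with SD τ, independently of background change, then r = √(0.065² + τ²)/0.065.
- τ = 0.02 gives r = 1.05. At 59 + 29, OLS type I error is 4.7%; power is 85.2% with OLS and 84.8% with HC3.
- τ = 0.03 gives r = 1.10. OLS type I error is 4.3%; power is 82.8% and 83.5%.
- τ = 0.046, as large as the target effect, gives r = 1.23.
- In reverse, r = 1.25 needs τ = 0.065 × √(1.25² − 1) = 0.049, and r = 1.5 needs τ = 0.065 × √(1.5² − 1) = 0.073.

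**The case against.** **Direction.** A reader might infer that varying response to CVC makes the primary p-value wrong in either direction, including false positives. The documents do not support that. Response that varies independently of background change adds variance to the larger arm, and the only consequence is a conservative test. If CVC does nothing in anyone, the variances are equal and the test is valid. Inflated type I error needs CVC to reduce spread, for example by lowering TBR most in those who would otherwise have risen.

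**Size.** A ratio of 1.25 needs an effect SD (0.049) above the whole target effect. With a mean effect of 0.046 and normal effects, about 17% of participants would then worsen on CVC. At ratios of 1.05 to 1.10, HC3 moves power by less than 1 point and can lose a little. Even at 1.25, most of the fall from 87.2% to 76.6% comes from the extra variance itself; HC3 recovers about 3 points and HC2 about 4.

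**Plausibility.** Protocol 2.1 expects near-maximal receptor blockade in most participants and calls the dolutegravir effect modest. The efficacy set requires at least 22 weeks on treatment. Analysis is on the log10 scale, where a constant proportional effect shifts the mean and adds no variance.

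**Is it really a gap?** Pooling is the default meaning of linear regression, not a stated assumption, and the Analysis Implementation Plan might specify otherwise. The arm-level intervals in SAP 7.2.1 would let a reader recover the SDs approximately, and the figure in SAP 7.2.2 shows changes by arm.

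All of this limits the size of the point. What stands is that the estimator behind the primary p-value is not named in the SAP, and that choosing it after seeing the arm SDs would be data-driven.

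**Conclusion.** The point holds as an inexpensive improvement, not as an error that invalidates the primary analysis. A plain regression in this 2:1 trial gives a standard error that is about 8% too large at a CVC/placebo SD ratio of 1.25 and about 7% too small at 0.8. If response to CVC varies, the first direction is the expected one: type I error about 3.5% and power about 77%, against 80–81% with robust standard errors at 59 + 29. At a ratio of 1.10 the gain is about 1 point. A type I error near 7% belongs to a different case, a less variable CVC arm, for which the documents offer no mechanism.

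These figures rest on assumed SD ratios, normal errors, 50% statin use and complete data. No figure in either document shows that the arm SDs differ.

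**What to change.** Before unblinding, add one sentence to SAP 7.2.3: the confidence interval and p-value for primary model (a) use HC2 or HC3 standard errors, or arm-specific residual variances, computed within each imputed data set before pooling. Name one of these as the primary choice. Add the SD of change by arm to the table in SAP 7.2.1.

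The point estimate does not change. If the variances are equal, HC3 costs about 1 power point (81.4% to 80.0% at 50 + 25; 87.2% to 86.2% at 59 + 29), and HC2 costs almost nothing. HC2 has somewhat higher power than HC3; HC3 holds type I error slightly better when the CVC arm is much less variable.

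Use in interaction model (b) is optional. It was checked only with equal SDs, where HC3 lowered power for an interaction of 0.046 from 33.7% to 31.8%, a larger cost than in model (a). Robust standard errors combined with multiple imputation were not simulated, so a short check on simulated data should precede the choice.
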